7.9 Concomitant Medications

Concomitant medications (prescription medications, over-the-counter medications including multi-vitamins and herbal remedies) must be reviewed for all subjects during screening and at every study visit. Vaccines (i.e., influenza, COVID-19) will only be allowed in the active treatment extension period.

If use of a permitted concomitant medication occurs during the study, subjects will be instructed to report all such medications taken and to report any changes to existing medications while on study through the follow-up period; it is the responsibility of the Investigator to ensure that details regarding the medication(s) are recorded in full in the subject's medical records.

Prohibited concomitant medications in this study are listed in Section 8.5.

7.10 Adverse Events

Adverse events (AEs) will be recorded and monitored for all subjects who are enrolled in the study (sign an informed consent form and receive at least one dose of study drug).

7.11 Modified Mayo Clinical Score (MMCS)

The Mayo Score will be determined within 2 weeks after Screening and following the Day 56 sigmoidoscopy to evaluate the potential efficacy of SPH3127 as a treatment for mild-to-moderate UC. The MMCS will also be determined at the end of the active treatment extension (D336). Stool frequency and rectal bleeding scores will be taken at the D56 and D336 visits; the endoscopy score will be determined from the sigmoidoscopy performed within 2 days of these visits. The Modified Mayo Score in this study does not include the Physician's Global Assessment component. Directions will be provided to patients on ratings of Stool Frequency and Rectal Bleeding and will be recorded on an electronic patient diary or by patient recall (at Screening). Patients may be sedated for flexible sigmoidoscopy which will be recorded and scored by a blinded central reader.

Components of the Modified Mayo Clinical Score:

Stool Frequency
0 = Normal
1 = 1-2 stools/day more than normal
2 = 3-4 stools/day more than normal
3 = >4 stools/day more than normal
Rectal bleeding*
0 = None
1 = Visible blood with stool less than half the time
2 = Visible blood with stool half of the time or more
3 = Passing blood alone
Mucosal appearance at endoscopy
0 = Normal or inactive disease
1 = Mild disease (erythema, decreased vascular pattern)
2 = Moderate disease (marked erythema, absent vascular pattern, friability, erosions)
3 = Severe disease (spontaneous bleeding, ulceration)

^{*}A score of 3 for bleeding requires patients to have at least 50% of bowel motions accompanied by visible blood and at least one bowel motion with blood alone.

7.12 UC-100 Score

The composite UC-100 score (i.e., $1+16 \times \text{Mayo}$ Clinic stool frequency subscore [0 to 3] + $6 \times \text{Mayo}$ Clinic endoscopic subscore [0 to 3] + $1 \times \text{Robarts}$ Histopathology Index score [0 to 33]), which ranges from 1 (no disease activity) to 100 (severe disease activity) will be calculated based on the respective subscores collected within 2 weeks after Screening and following the Day 56 sigmoidoscopy (within 2 days of visit). The UC-100 Score will also be determined at the end of the active treatment extension (D336; within 2 days of visit).

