7.13 Robarts Histopathology Index (RHI)

The Robarts Histopathology Index includes 4 grading domains: chronic inflammatory infiltrate, lamina propria neutrophils, neutrophils in the epithelium, and erosions or ulcerations. Lesion tissue samples will be graded according to this scale within 2 weeks after Screening and following the Day 56 sigmoidoscopy (within 2 days of visit). The

RHI will also be determined at the end of the active treatment extension (D336; within 2 days of visit).

Components of the Robarts Histopathology Index:

Chronic inflammatory infiltrate
0=No increase
1=Mild but unequivocal increase
2=Moderate increase
3=Marked increase
Lamina propria neutrophils
0=None
1=Mild but unequivocal increase
2=Moderate increase
3=Marked increase
Neutrophils in epithelium
0=None
1=<5% crypts involved
2=<50% crypts involved
3=>50% crypts involved
Erosion or ulceration
0=No erosion, ulceration or granulation tissue
1=Recovering epithelium+adjacent inflammation
1=Probable erosion—focally stripped
2=Unequivocal erosion
3=Ulcer or granulation tissue

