7.15 UC Histology Assessment

Samples of UC tissue will be taken at the time of flexible sigmoidoscopy. Tissue samples will be evaluated for histology (and graded using the MMCS and Robarts Histopathology Index) and tissue biomarker levels (e.g., angiotensin II, complement C3, cytokines IL-1 β , IL-17A, TNF- α , IL-6, and IL-23).

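### Does the unweighted layout of the Robarts index in Section 7.13 break the 0–33 range that UC-100 needs?

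*Combined protocol and SAP*

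**What the plan says.** Section 7.12 defines UC-100 as 1, plus 16 times the stool frequency subscore (0–3), plus 6 times the endoscopic subscore (0–3), plus 1 times the RHI. It gives the range of the RHI and of the composite as "Histopathology Index score [0 to 33]), which ranges from 1 (no disease activity) to 100 (severe disease activity".

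Section 7.13 says: "The Robarts Histopathology Index includes 4 grading domains". These are chronic infiltrate, neutrophils in the lamina propria, neutrophils in the epithelium, and erosion or ulceration. A table gives the grades, with 3 as the top grade in every domain. The instruction is: "Lesion tissue samples will be graded according to this scale". The section gives no multipliers, no rule for combining the grades and no total.

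Section 7.15 says the biopsy samples are "graded using the MMCS and Robarts Histopathology Index". The modified Mayo score (MMCS) defined in Section 7.11 has three items: stool frequency, rectal bleeding and endoscopic appearance. None is histological.

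RHI and UC-100 at week 8 are both on the list of efficacy and translational endpoints (Study Summary; Section 3). Section 10.4.3 says they will be analysed descriptively.

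**The concern.** Read one after the other, the two sections seem to describe different scales. Section 7.12 needs an RHI that reaches 33. The four domains in Section 7.13 appear to reach only 12, and no weights are printed anywhere in the document to close the gap.

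If a programmer added the printed grades, two listed endpoints would be wrong. The RHI would sit on a 0–12 scale, and histology would count for much less in UC-100 than the formula intends. The mistake could also go unnoticed, because every unweighted value still lies within 0–33 and 1–100, so an ordinary range check would pass it. The mention of the MMCS in Section 7.15 adds to the impression that the histology scoring was not set down with care.

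**Working it through.** **Inputs.** From Section 7.12: constant 1; stool frequency weight 16, subscore 0–3; endoscopy weight 6, subscore 0–3; RHI weight 1, range 0–33; stated UC-100 range 1–100. From Section 7.13: four domains, top grade 3 in each, no weights.

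**Step 1: the plan's own range.**
- Minimum: 1 + 16×0 + 6×0 + 0 = 1.
- Maximum: 1 + 16×3 + 6×3 + 33 = 1 + 48 + 18 + 33 = 100.

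The stated 1–100 is reproduced exactly, so Section 7.12 is consistent with itself.

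**Step 2: a plain sum of the printed grades.**
- Maximum RHI: 4 × 3 = 12.
- Maximum UC-100: 1 + 48 + 18 + 12 = 79, which is 21 points short.
- The erosion domain prints grade 1 twice. If that were a misprint and the domain ran 0–4, the RHI maximum would be 3×3 + 4 = 13 and the UC-100 maximum 80. This does not close the gap.

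**Step 3: shares of the UC-100 range under each reading.**

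| Component | RHI 0–33 (span 99) | Plain sum, RHI 0–12 (span 78) |
|---|---|---|
| Stool frequency | 48/99 = 48% | 48/78 = 62% |
| Endoscopy | 18/99 = 18% | 18/78 = 23% |
| Histology | 33/99 = 33% | 12/78 = 15% |

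These are shares of the theoretical range, not of the variation among enrolled patients. Entry requires an endoscopic subscore of at least 2 (Section 5.3), and severe disease is excluded (Section 5.4), so the sample will not fill the range. Stool frequency is the largest component under either reading.

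**Step 4: what the document implies about weights.** If RHI is a weighted sum of the four 0–3 grades, the weights must total 33/3 = 11. The text does not determine them. There are 120 ordered sets of four positive whole numbers that total 11, and four equal weights of 11/4 = 2.75 also do. It therefore cannot be inferred from the document that some domains count more than others.

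**Step 5: do the sections conflict?** Section 7.13 tells the pathologist how to grade each domain. Section 7.12 states the range of the resulting score. Both can be followed: grade by 7.13, then combine so that the result runs 0–33. A conflict appears only if one adds a rule, the plain sum, that neither section states. UC-100 cannot be programmed without reading Section 7.12, and that is where the 0–33 range stands.

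**The case for a change.** The best case for a change is that a plain sum is the natural reading. Section 7.11 sets out the MMCS in the same style, as items graded 0–3 without weights, and there a plain sum is meant: 3 × 3 = 9, which matches the upper end of the 4–9 entry criterion in Section 5.3. A reader could carry that habit over to Section 7.13. The document offers little to stop this. No reference is identified as a source for RHI or UC-100 scoring, no histology reader or scoring manual is named, and the blinded central reader is described only for the sigmoidoscopy. Histology also enters the planned correlation with tissue biomarkers, and with 10 patients per arm a diluted histology signal would be unwelcome.

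Much of this stands. The weights are absent, they cannot be recovered from the text, and a range check would not reveal the error. It remains a possible error rather than one the plan prescribes. For the MMCS the plain sum agrees with the printed limits; for the RHI it disagrees with the 0–33 printed in the preceding section. Section 4.1 also presents UC-100 and RHI as validated instruments, not scales devised for this trial, so the scoring rule belongs to the index. If the domain grades are kept, a wrong total can be recalculated without new data.

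A remedy drawn from this document could only say that the weights should be written down; it could not supply them. A test of the all-maximum and all-zero cases is ordinary programming validation and needs no protocol text.

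**Conclusion.** No change to the plan is needed. Section 7.13 leaves out the weights, the combining rule and the total range of the RHI. That is missing detail; no stated rule gives a wrong result. The figures of 12 for RHI and 79 for UC-100 hold only if the grades are simply added, which the plan does not say and which its own 0–33 range rules out.

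This rests on two assumptions that cannot be checked here: that whoever scores the slides or programs the endpoint applies the named index's own weighting, and that the individual domain grades are retained.

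The consequences of a slip would be limited. The primary objective is safety and tolerability (Section 2.1), no sample size calculation depends on these scores (Section 10.2), and neither RHI nor UC-100 is used for eligibility or for stopping. Section 10.1 does allow comparisons with placebo, so a wrong derivation would matter to the reader of those two endpoints, but it would be correctable. The reference to the MMCS in Section 7.15 is loose wording: Section 7.11 makes plain that the score has no histology item, so no value changes.

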7.13 Robarts Histopathology Index (RHI)

The Robarts Histopathology Index includes 4 grading domains: chronic inflammatory infiltrate, lamina propria neutrophils, neutrophils in the epithelium, and erosions or ulcerations. Lesion tissue samples will be graded according to this scale within 2 weeks after Screening and following the Day 56 sigmoidoscopy (within 2 days of visit). The

RHI will also be determined at the end of the active treatment extension (D336; within 2 days of visit).

Components of the Robarts Histopathology Index:

Chronic inflammatory infiltrate
0=No increase
1=Mild but unequivocal increase
2=Moderate increase
3=Marked increase
Lamina propria neutrophils
0=None
1=Mild but unequivocal increase
2=Moderate increase
3=Marked increase
Neutrophils in epithelium
0=None
1=<5% crypts involved
2=<50% crypts involved
3=>50% crypts involved
Erosion or ulceration
0=No erosion, ulceration or granulation tissue
1=Recovering epithelium+adjacent inflammation
1=Probable erosion—focally stripped
2=Unequivocal erosion
3=Ulcer or granulation tissue

7.14 Flexible Sigmoidoscopy

To prepare for flexible sigmoidoscopy, recommendations will be given to patients the day before the scheduled sigmoidoscopy at Screening (within 2 weeks of the Screening visit) and for the Day 56 site visit (within 2 days of visit). The same instructions will be

given to patients prior to the Day 336 site visit (within 2 days of visit), for those participating in the active treatment extension. The recommendations may include:

- Follow a special diet the day before the exam. Patients may be asked to not eat the day before the exam. Drinks may be limited to clear liquids plain water, broth, carbonated beverages, and tea and coffee without milk or cream. Patients may be asked not to eat or drink anything after midnight the night before the exam.
- Take a laxative the night before the exam.
- Use an enema kit. Patients will need to use an over-the-counter enema kit, typically a few hours before the exam to empty their colon.

During the exam, patients may be sedated. The sigmoidoscopy will be recorded and scored by a blinded central reader. There is a high degree of correlation in assessments of UC activity made by rectosigmoidoscopy vs. colonoscopy (Colombel et al., 2016).

7.15 UC Histology Assessment

Samples of UC tissue will be taken at the time of flexible sigmoidoscopy. Tissue samples will be evaluated for histology (and graded using the MMCS and Robarts Histopathology Index) and tissue biomarker levels (e.g., angiotensin II, complement C3, cytokines IL-1 β , IL-17A, TNF- α , IL-6, and IL-23).

7.16 Plasma Biomarkers

Blood samples (3 mL/time point) will be collected once at each time point (-10", 1', 2', 4', 8') for plasma biomarker (e.g., cytokines IL-1β, IL-17A, TNF-α, IL-6, and IL-23) analysis into anticoagulant tubes containing EDTA-K₂ and centrifuged for 15 min. The pretreated plasma biomarker plasma samples will be frozen and sent for determination of biomarker levels. Sample collection will occur over 8 hours at the study site on Days 1, 28 and 56.

7.17 SPH3127 Pharmacokinetics

Blood samples (3 mL/time point) will be collected once at each time point (-10" predose, 15", 30", 1', 2', 4', 8') for PK analysis into anticoagulant tubes containing EDTA-K₂ and centrifuged for 15 min. The pretreated PK plasma samples will be frozen and sent for determination of SPH3127 levels. Sample collection will occur over 8 hours at the study site on Days 1, 28 and 56.

8 STUDY DRUG MANAGEMENT

8.1 Description

8.1.1 Formulation

SPH3127 50 mg tablets or matching placebo tablets will be packed in blister cards (PVC with foil back) containing a 2-week supply (one tablet per day) plus 2 extra tablets to account for Visit scheduling (i.e., 2 x 8 configuration). Each blister card is packed individually in a foil pouch. Subjects will receive 2 blister cards (in foil pouches) for each 2-week period and will take one tablet orally from each blister card daily.

The study drug products (SPH3127 and placebo tablets) will be packaged with the following labeling information:

- serial number (for blinding and randomization)
- protocol number
- Sponsor's identification
- investigational new drug statement
- drug product name and potency
- drug product manufacturer
- route of administration
- instructions for use and storage
- precautionary statements

8.1.2 Storage

The supplied drug product should be stored at room temperature (15°C to 25°C).

8.2 Packaging and Shipment

The blister cards in foil pouches will be provided in cardboard packaging.

Access to study drug will be limited to designated study personnel.

Neither the Investigator nor any designees may provide study drug to any subjects who are not participating in this study.

8.3 Dose and Administration

A total of 30 eligible patients will be randomly assigned to one of three treatment arms (10 subjects per treatment group):

- Treatment A: 50 mg SPH3127 (given as one 50 mg tablet in the morning and one placebo tablet in the evening) PO daily for 8 weeks;
- Treatment B: 100 mg SPH3127 (given as one 50 mg tablet in the morning and one 50 mg tablet in the evening) PO daily for 8 weeks;
- Treatment C: Matching placebo tablets PO daily (one tablet in the morning and one tablet in the evening) for 8 weeks.

All randomized subjects will have the opportunity to enter an active treatment extension after the last main study visit (Day 56). Medication will be dispensed at 8-week intervals in the same 2-week blister packs as the main study for an additional 10 months in the active treatment extension. Those subjects receiving Treatment A (50 mg SPH3127 total daily dose) and who choose to enter the extension will continue on Treatment A in a blinded manner (will not know SPH3127 dose). Those subjects receiving Treatment B (100 mg SPH3127 total daily dose) and who choose to enter the extension will continue on Treatment B in a blinded manner (will not know SPH3127 dose). Those subjects receiving Treatment C (placebo) and who choose to enter the extension will be

randomized to receive Treatment A or Treatment B in a blinded manner (will not know SPH3127 dose).

8.4 Accountability

The study pharmacist or coordinator and clinical Investigator will maintain accurate records of receipt of all study drug, including dates of receipt. Study personnel will maintain accurate records regarding when and how much study drug is dispensed to and used by each subject in the study. Reasons for departure from the expected dispensing regimen must also be recorded. At completion of the study, to satisfy regulatory requirements regarding study drug accountability, all study drug will be reconciled and retained or destroyed according to applicable state and federal regulations and International Conference on Harmonisation (ICH) guidelines.

8.5 Prohibited Concomitant Therapy

Patients treated with oral mesalamine >2.5 g/d, systemic steroids or rectal steroids within 4 weeks prior to randomization, rectal mesalamine (within 2 weeks), immunomodulators or immunosuppressant drugs, including, but not limited to, IL-6 inhibitors, TNF inhibitors, anti-IL-1 agents and JAK inhibitors within 5 half-lives prior to randomization, antibiotics, anti-diarrheals (within 2 weeks), drugs blocking the renin-angiotensin system (e.g., direct renin inhibitors, angiotensin converting enzyme (ACE) inhibitors, or angiotensin II receptor blockers (ARBs)) (within 4 weeks) or administration of any investigational drug (within 4 weeks) will be excluded from the study. Because SPH3127 is a direct renin inhibitor with the potential to reduce blood pressure, other classes of antihypertensives (e.g., calcium channel blockers, beta blockers, diuretics, direct vasodilators, alpha blockers, central α2 antagonists) (within 4 weeks) will also be excluded from the study. These medications will also be prohibited during the study unless required to treat medical conditions and approved by the Medical Monitor.

Vaccinations are prohibited within 4 weeks of randomization and throughout the study (main and active treatment extension phases). Influenza and COVID-19 vaccinations are permitted during the active treatment extension phase of the study.

Although SPH3127 is mainly metabolized by CYP3A4, the impact of CYP3A4 inhibitors or inducers on SPH3127 PK has not been characterized in humans. Consequently, drugs, herbal medicines and substances that inhibit or induce CYP3A4 will be prohibited during the study. Examples of strong and moderate inhibitors and inducers of CYP3A4 include, but are not limited to:

- Strong inhibitors boceprevir, cobicistat, danoprevir, ritonavir, elvitegravir, grapefruit juice, itraconazole, ketoconazole, lopinavir, paritaprevir and (ombitasvir and/or dasabuvir), posaconazole, saquinavir, tipranavir, telithromycin, troleandomycin, voriconazole;
- Moderate inhibitors aprepitant, ciprofloxacin, conivaptan, crizotinib, cyclosporine, diltiazem, dronedarone, erythromycin, fluconazole, fluvoxamine, imatinib, tofisopam, verapamil;
- Strong inducers apalutamide, carbamazepine, enzalutamide, mitotane, phenytoin, rifampin, St. John's wort; and,

• Moderate inducers - bosentan, efavirenz, etravirine, phenobarbital, primidone.

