5.4 Exclusion Criteria

An eligible subject will not be enrolled in the trial if any of the following exclusion criteria are met:

- 1. Diagnosis of severe UC, defined as the presence of ≥ 6 bloody stools daily with one or more of the following: (1) oral temperature > 37.8°C or > 100.0°F; (2) pulse > 90 beats/min; (3) hemoglobin concentration < 10.5 g/dL; or erythrocyte sedimentation ratio (ESR) > 30.
- 2. Patients treated with oral mesalamine >2.4 g/d, systemic steroids or rectal steroids within 4 weeks prior to randomization, rectal mesalamine (within 2 weeks), immunomodulators or immunosuppressant drugs, including, but not limited to, IL-6 inhibitors, TNF inhibitors, anti-IL-1 agents and JAK inhibitors within 5 half-lives prior to randomization, antibiotics, anti-diarrheals (within 2 weeks), drugs blocking the renin-angiotensin system (e.g., direct renin inhibitors, angiotensin converting enzyme inhibitors, or angiotensin II receptor blockers) (within 4 weeks) or

administration of any investigational drug (within 4 weeks). Because SPH3127 is a direct renin inhibitor with the potential to reduce blood pressure, other classes of antihypertensives (e.g., calcium channel blockers, beta blockers, direct vasodilators, alpha blockers, central α2 antagonists) (within 4 weeks) will also be excluded. Drugs, herbal medicines and substances that inhibit or induce CYP3A4 (e.g., ritonavir, itraconazole, grapefruit juice) (within 2 weeks or 5 half-lives, whichever is longer) will be excluded.

- 3. History of colectomy or partial colectomy, colorectal dysplasia, Crohn's disease, toxic megacolon, or bleeding disorders.
- 4. A stool sample positive for enteric pathogens, including *Clostridium difficile*.
- 5. Patients with an estimated glomerular filtration rate (eGFR) \leq 60.
- 6. Patients with hepatic impairment or history of liver cirrhosis.
- 7. Serum creatinine > 1.5 times the upper limit of normal, aspartate aminotransferase (AST), alanine aminotransferase (ALT), total bilirubin (TBIL) or alkaline phosphatase (ALP) > 2 times the upper limit of normal.
- 8. Serious underlying disease other than UC.
- 9. Previous participation in clinical trials with SPH3127
- 10. Known hypersensitivity to tablet ingredients or history of a significant allergic reaction to any drug as determined by the investigator.
- 11. Known seropositivity or positive test at screening for an active viral/bacterial infection with:

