6.3 Premature Discontinuation

An enrolled subject is defined as having signed an informed consent, met all inclusion/exclusion criteria, been randomized to treatment and having received at least one dose of study drug.

A subject has the right to withdraw from the study at any time for any reason without prejudice or without jeopardizing their medical care. The Investigator must withdraw the subject from the study if the subject requests to be withdrawn.

The Investigator may discontinue a subject from the study when, in his/her judgment it is necessary for any reason, including any of the following:

- Adverse event (serious or non-serious);
- Failure to comply with the protocol;
- Requires a medication that is specifically prohibited by the protocol; or,
- It is in the subject's best interest.

The Investigator may also withdraw a subject upon the request of the Sponsor, or if the Sponsor terminates the study for clinical or administrative reasons.

If a subject is withdrawn from participation in the study, the reason(s) for discontinuation shall be documented. A subject who discontinues the study early (regardless of cause) will be requested to return to the clinic and have all the early termination assessments

performed. If a subject is discontinued from study due to an adverse event, the subject will be followed until the event is resolved or deemed clinically stable.

A subject that has been met all the eligibility criteria at Screening, but not at baseline (Day 1), will be replaced. A subject that has enrolled in the study (signed informed consent, met all inclusion/exclusion criteria, has been randomized and received at least one dose of study drug) that discontinues from the study (for any reason) will not be replaced.

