10.4.4 Clinical remission/response, Endoscopic remission/response

Descriptive statistical methods will be used to analyze the data from definitions of clinical remission and response, and endoscopic remission and response.

Clinical remission:

Defined as a MMCS of 0-2, including the following three components:

- 1. Stool frequency subscore = 0 or 1;
- 2. Rectal bleeding subscore = 0; and,
- 3. Endoscopy subscore = 0 or 1.

Clinical response:

Defined as a decrease from baseline in MMCS of ≥ 2 points AND a 30% reduction from baseline PLUS a decrease from baseline in rectal bleeding subscore of ≥ 1 or an absolute rectal bleeding subscore of ≤ 1 .

Endoscopic remission:

Defined as an endoscopic subscore = 0.

Endoscopic response:

Defined as a > 1-point reduction in endoscopic subscore.

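### Week 8 remission and response ignore added colitis therapy, although oral mesalamine below the cap may be changed freely and other colitis drugs may be approved on study

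*Combined protocol and SAP*

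**What the plan says.** **Oral mesalamine.** The exclusion list in Section 5.4 opens with "Patients treated with oral mesalamine >2.4 g/d"; Section 8.5 opens with "Patients treated with oral mesalamine >2.5 g/d". Neither section, nor any other, requires the dose to be stable before randomization or fixed through Week 8. Section 7.9 asks only that medication changes be reported and entered in the medical record.

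**Other colitis drugs.** Section 8.5 lists systemic and rectal steroids, rectal mesalamine, immunosuppressants, anti-diarrheals and others, and then adds: "These medications will also be prohibited during the study unless required to treat medical conditions and approved by the Medical Monitor".

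**What follows if such a drug is needed.** Section 6.3 is permissive: "The Investigator may discontinue a subject from the study when, in his/her judgment it is necessary for any reason". One of its listed reasons is "Requires a medication that is specifically prohibited by the protocol".

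**Outcome definitions.** In Section 10.4.4, clinical remission is "Defined as a MMCS of 0-2, including the following three components" (stool frequency 0 or 1, bleeding 0, endoscopy 0 or 1). Clinical response needs a fall in the modified Mayo score (MMCS) of at least 2 points and 30%, plus either a fall of at least 1 in bleeding "or an absolute rectal bleeding subscore of" 1 or less. Endoscopic remission and response use the endoscopic subscore only. No definition refers to medication. The analysis is stated as "Descriptive statistical methods will be used to analyze the data from definitions of clinical remission and response". Section 10 contains no rescue-therapy, intercurrent-event or non-responder rule.

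**The concern.** Read together, these sections let a patient receive effective colitis therapy beyond the study tablets, remain on study, and be counted at Week 8 as though the tablets alone had produced the result. Added therapy in the placebo arm hides a drug effect; in an active arm it mimics one. Blinding and central endoscopy reading protect the scoring. They do not stop treatment being given because a patient is doing badly, and that need may differ by arm if the drug works.

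The primary objective is safety. But Section 4.1 makes disease-activity scores part of the pharmacodynamic assessment, the Study Summary says the trial should give early signs of efficacy, and Section 10.1 plans comparisons of placebo with each dose and with both doses pooled. What is at stake is how clearly the Week 8 rates can be read for the next development decision.

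**Working it through.** The plan states no power, response rate or rate of added therapy (Section 10.2), so there is no figure of its own to reproduce.

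**1. Routes by which added therapy can reach the outcome**
- Oral mesalamine started or raised below the cap: no approval needed, no breach, no withdrawal trigger, no effect on classification.
- Listed drugs: barred by default, possible with medical need and Medical Monitor approval; withdrawal optional; no effect on classification if the patient stays.
- Timing: the schedule puts the baseline sigmoidoscopy within 2 weeks after Day -28, that is, up to about Day -14. A mesalamine increase between that examination and Day 1 could also appear as improvement from baseline.

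**2. Weight of one patient** (10 per arm, Section 4.1)
- One arm: 1/10 = 10 points. Pooled active doses: 1/20 = 5 points.
- Illustration with assumed counts and a two-sided Fisher exact test (the plan names no test): 5/10 vs 0/10 gives p = 0.033; with one active success reclassified, 4/10 vs 0/10 gives p = 0.087.

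**3. Which outcomes can change through stool frequency alone**
- Inclusion criterion 4 requires bleeding at least 1, endoscopy at least 2 and MMCS 4 to 9. Stool frequency 0–3, bleeding 1–3 and endoscopy 2–3 give 4 × 3 × 2 = 24 profiles; the one summing to 3 is ineligible, leaving 23.
- Lower only stool frequency, and require a fall of at least 2 points and 30% with bleeding at most 1. In the order stool frequency, bleeding, endoscopy:
  - (2,1,2): 2 of 5 = 40%, qualifies.
  - (2,1,3): 2 of 6 = 33%, qualifies.
  - (3,1,2): 2 of 6 = 33%, qualifies.
  - (3,1,3): 2 of 7 = 29% fails; 3 of 7 = 43% qualifies.
- So 4 of 23 profiles can reach clinical response with bleeding and mucosa unchanged. These are profiles, not patients, and give no probability.
- Clinical remission cannot be reached this way, because it needs bleeding 0 and endoscopy at most 1.
- UC-100 = 1 + 16 × stool frequency + 6 × endoscopy + Robarts index, range 1 to 100 (Section 7.12). One stool-frequency grade is 16 of 99 points (16%); two grades are 32 points.

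**4. Size under assumed rates** (not in the documents)
- Let f be the share of an arm receiving added therapy and s the share of those made successes by it. The expected rise in the arm's rate is f × s.
- Low: 0.05 × 0.25 = 1.25 points. High: 0.20 × 0.50 = 10 points.
- Chance of at least one such success among 10 = 1 − (1 − f × s)^10: 0.118 (low) to 0.651 (high).

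**5. Scale against sampling error** (30% and 10% are illustrative)
- 1.96 × √(0.3 × 0.7/10 + 0.1 × 0.9/10) = 1.96 × √0.030 = 0.339, about ±34 points.

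**The case against.** The strongest defence is proportion. The efficacy endpoints are exploratory, Section 10.4.4 is descriptive, no decision rule depends on these rates, and even the high assumed bias of 10 points is well inside ±34 points of sampling error. That stands, and it limits the weight of the point. It does not remove it: sampling error is unavoidable at this size, whereas an undefined outcome is not, and a rule chosen after unblinding would be chosen where one patient matters.

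A second defence is that the listed drugs are already controlled. They need both medical need and approval, and needing one is a named reason for withdrawal. The exception also covers a mixed list, including antihypertensives and antibiotics, so the conditions it has in mind may be other than colitis. This also stands in part. A reader might infer that prohibited colitis drugs are freely available on study; the text does not support that. Nor does it exclude colitis from the exception, and none of this touches oral mesalamine below the cap, which is the uncontrolled route.

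Third, the stool-frequency example is remote: an anti-diarrheal must be approved, the patient must stay, and stool frequency must fall by at least two grades. Agreed. It shows that the definition permits this result, not that it is likely.

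Fourth, counting added therapy as failure is one legitimate strategy and treatment policy is another. True. For asking what the tablets did, the former is the better main summary, with the score-only version kept alongside.

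**Conclusion.** The gap is real and worth a cheap correction. As written, improvement on added colitis therapy counts as a success of the assigned arm, and each such patient is worth 10 points in an arm of 10 (5 points pooled). That much follows from the documents. The expected shift of 1.25 to 10 points rests entirely on assumed frequencies.

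A reader might go further and conclude that the trial is biased in favour of SPH3127, or that its efficacy results will be invalid. The documents support neither: the direction depends on which arm receives more added therapy, its frequency is unknown, and safety is the primary objective. The effect is modest and confined to interpretation of the proof-of-concept signal.

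**What to change.** 1. **Sections 5.4 and 8.5.** Use one mesalamine cap. Require that oral mesalamine not be started or increased from the baseline sigmoidoscopy through the Week 8 assessment. A patient who changes it before randomization is not randomized unless baseline is repeated. This has to be set in advance, because analysis cannot restore a stable background dose afterwards.
2. **Section 10.4.4.** For the binary efficacy endpoints, count as a non-responder any patient who, after randomization and before the Week 8 assessment, starts or raises oral mesalamine, or receives steroids, rectal mesalamine, or immunosuppressants, biologics or JAK inhibitors for ulcerative colitis. List use for other conditions separately and decide its handling while blinded, so that a steroid course for an unrelated illness is not automatically a colitis failure. For endpoints that use stool frequency, also count anti-diarrheal use in the diary days behind the Week 8 score; the plan does not name those days, so name them.
3. **Reporting.** Add a score-only (treatment-policy) sensitivity summary and tabulate colitis medication changes by arm.

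The cost is a short amendment with IRB approval and slightly lower response rates. Medications are already reviewed at every visit (Section 7.9), but that section places the details in the medical record, so confirm that dose, dates and indication reach the CRF. The non-responder rule governs classification only and does not prevent a patient from being treated.
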